### **Exercise program**

For the first month of the exercise intervention we will conduct only *strength* and a few *balance* exercises to rehabilitate our participants. After the first month, and once our participants feel comfortable, we will incorporate *aerobic and additional balance exercises*. We will personalize participant programs based on baseline levels and increase them gradually. The exercise session will be conducted 50 minutes 3 times a week. Between sets there is a 60-second break.

- **Warmup and Activity (5 minutes)** The warmup consists of marching in place followed by a brief group aerobic activity.
- **Strength exercises (30 minutes 3 days a week):** The strength exercises will focus on the major muscle groups (chest, shoulders, arms, back, abdomen, and legs) and will use resistance bands for each exercise. The participant will progress to a harder band when the exercise becomes easy, or are able to complete both sets without strain.
- **Balance Exercises (10 minutes 3 days a week):** We will incorporate common balance exercises, including those proven in a randomized trial, developed by [name], to improve physical performance in seniors. (RP [46](#), [47](#)) Some of these exercises include: Woodchop, Superman Pose and Straight-line walking.
- **Cool Down Activity (3-5 minutes):** Participants will complete a brief cool down activity that includes flexibility exercises and stretching following each exercise session.
- **Aerobic exercises:** After the first month of intervention, the coaches and Group leaders will help participants work towards 150 minutes a week of aerobic exercise. Participants will be educated on different aerobic activities (e.g. walking, dancing, games) they can do within their home and community.

### **Starting a new exercise site**

For the first week the coaches will:

- a. Attend each exercise session and observe the group leaders leading the class. The exercise coach will observe each group leader and provide continuous support, as needed.

For weeks 2-6 of the new site, the coaches will attend the exercise sites weekly. During this visit the coaches will:

- a. Make sure the site has all of the required materials.
- b. Meet with the group leader and answer questions.
- c. Work with the participants on progression and form.
- d. Perform chair stand test, arm curl test, single leg stance test, and make pedometers available to participants (monthly)
- e. Collect participant data.

For weeks 7-12 of a new site, items a through e will be done bi-weekly. After the 12th week of a new site, items a through e will be done monthly. Coaches will continue site visits to ensure program fidelity and to provide feedback to Group Leaders.

### **Exercise coaching**

For the first 4 weeks of the intervention the coaches will:

- a. After randomization occurs, the coach will call participants in the intervention group for introduction and to learn more about the participant and any medical conditions that may be important for the exercise coach to know. If the coach learns of any serious medical events or hospitalizations since baseline they will follow the return to exercise protocol and present the case to a PI through adverse event reporting in REDCap.
- b. Contact the patients by weekly phone calls or during site visits(duration of call: approximately 5 minutes) to give exercise tips, discuss goals and progress toward goals, injuries, soreness, and enjoyment.
- c. Conduct site visits to assure program fidelity, provide quality control feedback to volunteer Group Leaders.

For weeks 4-8 of the intervention coaches will follow item b, but instead of every week they will perform them bi-weekly.

After the 8th week of intervention coaches will follow items b & c, performing these items every month.

The coaches will meet regularly with group leaders and will supervise sessions on a rotating basis. If the participant misses 3 consecutive classes without notifying exercise coach, or the group leader expresses concerns for a participant, the coach will perform a check-up call between the regularly scheduled calls. Coaches will provide ongoing support and monitor the safety of the program for all participants.

### **Fitness Testing**

In order to capture the participant's progress, the participant will perform fitness tests once a month that will be shared with their PCP via regular progress reports. Each fitness test is based off of exercises already performed in the program. The 3 fitness tests are:

- a. 30 second chair stand test
- b. 30 second arm curl test
- c. Single leg stance test

### **Regular Progress Reports**

Every month the coach will record steps from the pedometer, patient adherence to exercise sessions, and measure functional fitness and strength (30 second chair stand test, 30 second arm curl test, and single leg stance test). The purpose of these activities is to provide feedback (via fax or electronic health record) to PCPs, considered key for integrating exercise coaching into primary care and the standard of care after referral to a specialist (e.g., cardiologist) (53).

### **Exercise program at home and/or community sites**

Our study design is to be "pragmatic", therefore, the intervention is designed to be something that the vast majority of people would be interested in, and we know that some people are shy and avoid group programs or do not like to travel. For that reason we have created an "at home" option, which will include the same exercises at the same times, but via DVD. Participants who regularly attend class, but may miss a session due to vacation or other obligations and insist on doing the exercises remotely, may be given the home exercise manual if they don't have

access to a DVD player. The home exercise manual can be used as a reminder for the proper way to perform the exercises that they have already learned and reviewed with their exercise coach. The manual is not intended to replace the Band Together sessions or Band Together DVD. This allows “choice” to be part of the study, though it will be a limitation as well. Giving people options is important and is part of standard clinical care, which this study – a pragmatic clinical trial – is designed to approximate.

Patients will have the choice to participate at home and/or at community sites and can modify that ratio as they choose. As a key secondary outcome is loneliness, the coach will encourage participation at community sites, but patients will choose.

The “at home” option for the exercise session will also be heavily utilized during times that our in-person community exercise sessions may be canceled due to circumstances outside of the study’s control. These circumstances may include weather related cancellations, disease outbreaks and/or recommendations from Penn State University or Milton S. Hershey Medical Center to stop in-person visits. When these circumstances arise, we will contact intervention participants and encourage them to participate in the DVD portion of the program. Exercise Coaches will continue to make contact with the research participants during these cancellations to ensure exercise are being done properly and to collect adverse events, as needed.

For the individuals who want to exercise at home, we will distribute the exercise DVDs every 9 months and the coach will continue to contact them, just as if they were joining the group. Coaches, over the phone and in-person at community sites, will encourage group participation, based on the belief that the social opportunities in groups reduce loneliness and depression. The main goal, however, is to encourage exercise, where people do it matters less.

If a participant wants to do the exercises at home, but does not have a DVD player, we will provide him/her a DVD player for the duration of their participation in our study. Upon completion of the study, the participant will return the DVD player during his/her 36 month follow-up visit. If the participant chooses to withdraw from the study, he/she will be asked to return the DVD player by mail or by dropping it off at one of our active exercise sites.

In the event of exercise sessions being canceled at our sites, we will offer optional Zoom exercise sessions to our participants to complete their exercises at home. The Zoom exercise session will be hosted and led by our trained exercise coaches. If a participant is interested in joining our Zoom exercise sessions they will be provided with instructions on how to connect to our HIPAA compliant Zoom session. The exercise coach will lead the exercise session with the same instructions and exercises that are on the DVDs.

At any time during the study at home participants are welcome to join any exercise site to continue the program.

If a participant does not have a computer or access to the internet, we will provide tablets and data plans for those who want to exercise virtually, for the duration of the study. Upon completion of the study, we will attempt to collect the tablets back by calling the participant over the phone and sending a prepaid mailer or collecting them in-person if applicable. If participant continues as a community member, they will be allowed to use

the tablet until the study end date.

#### **Community Members – *Nonrandomized exercise participants***

Once the community members consents to the research study, and obtain PCP permission to participate, they will have access to:

- The same group leader led exercise program as the intervention participants with the exception of access to an exercise coach.
- Zoom exercise sessions
- *Paper-based Exercise Trackers* that list the rules for progression and help track the community member's progression over time. These trackers are for optional use and will not be collected by the research staff.
- A set of resistance bands if they do not their own.
- If a community members does not have a computer or access to the internet, we will provide tablets and data plans for those who want to exercise virtually, for the duration of the study. Upon completion of the study, or withdrawal from the study, we will attempt to collect the tablets back by calling the community members over the phone and sending a prepaid mailer.

#### **7.2.6.4 Strategies for Promoting Adherence in the Physical Activity Group**

To keep participants engaged and adherent in the Physical Activity Group, the following strategies will be implemented at each site

1. **Rotation of balance exercises** – The balance exercises will be cycled through at a frequency determined by each exercise site, so that it adds variety to each exercise session.
2. **Monthly themes** – Each month the exercise coach will introduce a theme to each exercise site. The theme can include educational materials, a monthly challenge, and/or a monthly activity. An example of these monthly challenges could include encouraging participants to take advantage of the nice weather and go for a walk in their community or participating in outdoor activities that could not be done during winter months.
3. **A WISE Study Facebook Group**- A Facebook group will be created for intervention participants to join, if they would like. This group will be used to communicate with other participants across exercise sites. All posts in the group will be voluntarily made by participants, and they do not need to join if they wish not too. Additionally, pictures of research participants may be added by staff for functions such as holiday parties. Only participants with a signed media release form will appear in the photos.
4. **WISE Study Cookbook**- A cookbook was created with recipes submitted by intervention participants. This cookbook will be compiled by research staff and provided to intervention participants who would like a copy. The idea for this cookbook is for intervention participants to share recipes and to help build a broader sense of community within the study. Recipes were submitted on a voluntary basis.

#### **7.2.7. Phone Follow-ups**

##### **Group leaders**

Every 3 months the Exercise Coach will call, talk to in person, or email the Group leaders to complete a survey to ask about how they feel status of the group they are leading.

##### **Participants**

Every 4 months we will call the participants asking questions about the main outcome (SFRI), hospitalization or emergency department visit. A fall calendar will be given to the participant to record all fall events (e.g., date, location). This will help participants to recall falls during the 4 month period. In

addition, this will allow medical records to be requested, using a signed authorization form (part of the consent form). We will review all relevant Electronic Health Records (EHR) information, such as hospital and emergency department discharge summaries, outpatient visit notes, consultation notes, physical exam notes, dictated radiologist notes and plain film radiography.

We will ask questions related to adverse events using the adverse event form.

### **Community members**

Every 3 months the community members will be emailed a REDCap survey, 'Community Member AE and Satisfaction Survey' asking a few satisfaction survey questions and if they have had an adverse event in the last three months. If the community member does not respond to the survey, an exercise coach will call in an attempt to complete the survey. If the participant does report an adverse event, an adverse event form will be completed and reviewed by a study physician within 15 business days of staff being made aware of the adverse event.

### **7.2.8. Visit 2 and 3 – 12- and 24- Month Phone Follow-up**

At years 1 and 2, a telephone follow-up call will be done by a research assistant to collect a brief set of questions and to identify patients who have had a FF/SFRI, hospitalization or emergency department visit. This call will take about 15 minutes. For any subjects with a FF/SFRI or hospitalization/ED use, details about the event (e.g., date, location) will be asked. This will allow medical records to be requested, using a signed authorization form (part of the consent form). We will review all relevant EHR information, such as hospital and emergency department discharge summaries, outpatient visit notes, consultation notes, physical exam notes, dictated radiologist notes and plain film radiography. In addition, staff will notify participants and their PCPs of any critical values from the PROMIS questionnaire sections for anxiety and depression at the 12 and 24 assessment calls, and for PROMIS anxiety and depression scores.

Research staff will mail an answer guide for the 12 and 24 month assessments with each participant's falls calendar, starting with the 2019 calendar mailed in December, 2018. Having a visual guide to the questions and response choices will aid both the participant and study staff in responding to questions and collecting data.

We will ask questions related to adverse events using the adverse event form.

After completing the phone follow-ups, participants will receive \$25 each time.

### **7.2.9. Visit 4 – 36-Month Follow-Up Visit**

#### **Group leaders**

At 36-month, Group leaders will receive a telephone follow-up by the research coordinator to collect a brief set of measurements (same questions as baseline) and the net promoter score. This call should not take more than 20 minutes.

Group leaders will receive \$100 for completing the 36-months follow-up.

#### **Participants**

Participants will complete their 60 minute follow up visit with research staff at Penn State Hershey.

Prior to the 36-month visit, research staff will send participants the following questionnaires, to be completed at home and brought with them to the 36-month assessment: fear of falling, self-reported health, PROMIS 29: depression, anxiety and physical function, fatigue, pain, sleep disturbance, ability to participate in social roles and activities, brief loneliness questionnaire, physical activity, social domain (caregiver), VSPPB and assistive devices. The participant will also be asked to bring along a list of their current medications. These surveys should take approximately 20 minutes to complete.

Research staff will take the participant's blood pressure, height and weight. Research staff will then have the participant complete the 30 second chair stand test, 30 second bicep curl test to measure strength and review medications. Research staff will notify participants and their Primary Care Providers of a critical value for the PROMIS depression and anxiety measures, and of high blood pressure at the 36-month visit.

Research participants who are unable to attend an in-person visit due to extreme circumstances will be given the opportunity to complete a portion of the visit remotely via a telephone call with research coordinators. These circumstances include but are not limited to, travel burden, severe weather, disease outbreak and any recommendations by Penn State University or Penn State Milton S. Hershey Medical Center to stop in-person visits. These remote visits will not include the collection of the participant's blood pressure, height and weight or fitness testing.

Participants will receive \$75 for their participation.

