## 1.0 Objectives

### 1.1 Study Objectives

**AIM 1.** To compare the effectiveness of exercise coaching with enhanced usual care in reducing serious fall-related injuries (SFRI), including fragility fractures from a fall, among older adults with a prior fragility fracture. We hypothesize that 13% of control subjects will experience a SFRI versus 7% of exercise subjects after the 36 months.

**AIM 2.** To compare the effectiveness of exercise coaching versus enhanced usual care on other patient-centered outcomes (total number of falls, loneliness, physical function, muscle strength, bone density, and muscle mass) that patients told us they were interested in. We hypothesize that exercise coaching will significantly improve each of these outcomes.

**AIM 3.** To examine heterogeneity of treatment effects (HT-1) with regard to key participant factors (age, gender, race, ethnicity, osteoporosis medication use, intervention engagement, patient choice of exercise location – in-home v. community). We hypothesize that sub-groups can be identified for whom a particular intervention approach is most effective, to help inform patient-, provider- and key stakeholder decision makers. Of note, many of these subgroup analyses are not fully powered, particularly given the reduction in sample size from the original 2100 to the modified 1130. There is, as a result, less than 80% power to detect significant differences for most of these subgroup analyses. These analyses will, however, suggest where differences lie that can be further evaluated in future studies.

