### 1.2 Primary Study Endpoints

#### **Serious Fall-Related Injuries (SFRI), including Fragility Fractures from a fall**

To identify our main outcome (SFRI, including FF), we will collect main outcome data every 4 months and during the assessment (12, 24, 36 months) using a fall calendar to record all fall events (e.g., date, location). This will help participants to recall falls during the 4 month period. Subjects will be asked, for example, *“Have you fallen in the past 4 months (or since last contact)? Were you injured in any fall in the past 4 months (or since last contact)?” “Did you land on the floor, ground or other lower level when you fell?” “When you fell, did you break or fracture a bone? or “Were you told by a doctor, or other health professional”*. For any new events, the circumstances regarding the incident (i.e., what occurred) will be recorded for use in adjudicating whether the injury was related to a FF (i.e., “low-trauma” or fall from standing height or less). The dates of injuries and the name of the institution will be recorded, so that medical records can be sought using the authorization form signed by all patients at baseline.

For any SFRI (including FF) or hospitalization/ED visits noted quarterly or during the 12, 24 or 36 months assessment, medical records will be obtained, including outpatient notes, emergency department notes, hospital discharge summary reports and radiologic notes. All outcomes (e.g., SFRI) require evidence from medical records to be counted.

These records will be collected and presented, blinded to treatment condition, 14 days before the monthly meeting to the Outcomes Committee ([name]-Chair, [name], [name], [name], [name]). For each event, the Outcomes Committee will be charged with determining whether it was 1) a fracture related to a fall from standing height or less, 2) a non-traumatic fracture not related to a fall, 3) a serious fall related injury without a fracture, 4) a traumatic fracture (e.g., MVA), 5) a non-serious fall related injury, or 6) none. A vote is made for each event. If there is not agreement, it will be opened for discussion and another vote. If

consensus is not possible, the case will be presented to [name] [name] for final adjudication, given her vast experience with this process (34, 77, 78).

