### **7.2.6.3. Randomization**

Once eligible participants who sign the informed consent and completed the baseline questions, research staff at each site will randomize the participant into one of two groups (control, enhanced usual care; or intervention groups, enhanced usual care plus coached exercise program) in a one-to-one ratio. Stratification factors for randomization will be study site location (1=Penn State, 2=University of Pittsburgh, 3=Temple University), gender (0=female, 1=male), and bisphosphonate and other potent medication use (0=never, 1=ever). The research staff will conduct the randomization during the baseline visit through REDCap.

Participants randomized to the intervention group will also receive an introductory letter from their exercise coach with picture/name and details on a forthcoming phone call.

Group leaders, community members, and Spanish Speaking Interview members will not be randomized.

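### Masking is stated only for the Outcomes Committee: the staff who make the outcome calls and run the month-36 strength tests are neither masked nor separated from coaches or randomising staff

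*Combined protocol and SAP*

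**What the plan says.** Section 1.2 contains the only masking statement in the document. Medical records go to the adjudicators masked: "These records will be collected and presented, blinded to treatment condition, 14 days before the monthly meeting to the Outcomes Committee".

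The other steps that produce outcome data are described without one:

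- **Randomisation (7.2.6.3).** "research staff at each site will randomize the participant into one of two groups", and this happens at the baseline visit: "The research staff will conduct the randomization during the baseline visit through REDCap".
- **4-monthly calls (7.2.7).** "Every 4 months we will call the participants asking questions about the main outcome (SFRI), hospitalization or emergency department visit". The caller is not identified.
- **12- and 24-month calls (7.2.8).** "a telephone follow-up call will be done by a research assistant to collect a brief set of questions".
- **Month-36 visit (7.2.9).** "Research staff will then have the participant complete the 30 second chair stand test, 30 second bicep curl test to measure strength". Remote visits are telephone calls by research coordinators and omit fitness testing.

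The Aim 2 outcomes in section 1.1 are "total number of falls, loneliness, physical function, muscle strength, bone density, and muscle mass", so falls and strength both carry hypotheses.

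Section 1.2 requires medical-record evidence for any counted outcome. It obtains records for events, hospitalisations or emergency visits noted at the periodic contacts and annual assessments. Claims access is sought with the participant's permission. The participant flowchart (7.2.1) lists PaTH Network utilisation data at months 12, 24 and 36, and sections 8.2 and 8.3 plan a health-record search for those lost to follow-up.

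**The concern.** Masked adjudication protects how an event is classified, not whether it is found. Records are requested largely because something surfaced in a call. If a caller who knows the arm probes harder in one group, the primary event count shifts before the committee sees anything.

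The 30-second chair stand and arm curl depend on effort, so a tester's encouragement can move the score directly. Self-reported falls depend on how the question is asked and followed up. Participants cannot be masked to exercise coaching, which leaves assessor masking as the available protection against assessor bias.

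Several procedures make unmasking likely. Table 1 gives coaches participant phone calls and data entry. Coaches give the same chair-stand and arm-curl tests in the exercise arm every month (Starting a new exercise site; Fitness Testing). A loaned DVD player is returned at the 36-month visit. Section 10.0 has staff ask at every follow-up whether the program caused harm.

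**Working it through.** **Inputs from the plan.** SFRI 13% control and 7% exercise at 36 months (1.1); two-sided alpha 0.05; 1:1 allocation; 1130 enrolled, 15% lost, 960 remaining (8.3), so n = 480 per arm. The plan gives no detection rates and no SD for the strength tests; values for those are assumptions, shown over a range.

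**Step 1: reproduce the plan's power.** With control rate a, exercise rate b, d = a − b and p̄ = (a + b)/2:

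- SE0 = √[2p̄(1 − p̄)/n]; SE1 = √[(a(1 − a) + b(1 − b))/n]
- Probability of rejecting in favour of exercise = Φ[(d − 1.96·SE0)/SE1]

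For a = 0.13, b = 0.07: SE0 = 0.01936, SE1 = 0.01927, and (0.06 − 1.96 × 0.01936)/0.01927 = 1.144, giving 0.874. The stated 87% reproduces. Freedman's log-rank formula with 480 × 0.20 = 96 events and hazard ratio ln(0.93)/ln(0.87) = 0.521 gives 0.870.

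**Step 2: true null, exercise-arm events found less completely (assumed).** Both true rates are 13%; the exercise arm shows 0.13r.

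| Relative detection r | Observed exercise rate | Rejects in favour of exercise (nominal 2.5%) |
|---|---|---|
| 0.95 | 12.35% | 4.9% |
| 0.90 | 11.70% | 8.9% |
| 0.85 | 11.05% | 15.1% |

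For r = 0.90: d = 0.013, SE0 = 0.02124, SE1 = 0.02123, z = −1.348, Φ = 0.089. At a loss of only 3% (r = 0.97) the figure is 3.8%.

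**Step 3: planned effect true, exercise-arm events found more completely (assumed).** Coaches ask exercise participants about injuries (Exercise coaching), so this direction is equally open.

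| Relative detection r | Observed exercise rate | Observed risk ratio | Power |
|---|---|---|---|
| 1.00 | 7.00% | 0.54 | 87% |
| 1.05 | 7.35% | 0.57 | 83% |
| 1.10 | 7.70% | 0.59 | 77% |
| 1.20 | 8.40% | 0.65 | 64% |

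**Step 4: encouragement effect on a strength test, no true difference (assumed).** For a shift of δ SD and m tested per arm, the probability of rejecting in favour of exercise is about Φ[δ√(m/2) − 1.96].

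- δ = 0.05, m = 480: 0.05 × √240 = 0.775; Φ(−1.185) = 12%
- δ = 0.10, m = 480: 0.10 × √240 = 1.549; Φ(−0.411) = 34%
- δ = 0.05, m = 300: 0.05 × √150 = 0.612; Φ(−1.348) = 9%

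The last line shows the effect of testing fewer people in person, since remote visits omit the tests.

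**The case against.** The strongest reply is that the protocol is silent rather than unmasked. No section says that callers or testers are the people who randomised, or that they can see allocation in REDCap. Section 7.2.8 already gives the annual calls to a research assistant, Table 1 lists no outcome-assessment duty for coaches, and section 16.5 mentions a working protocol that may cover this. That stands. A reader might infer that one staff pool randomises, holds the allocation and then assesses; the text does not establish this. Nor is randomisation by site staff a concealment fault, since it runs through REDCap after the baseline questions.

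The second reply is that SFRI is well defended. Records are required, any hospitalisation or emergency visit triggers a request, PaTH data need no patient time, claims are sought, a fall calendar and set questions are used, and interviews are audited (2.3, 18.5). This also stands in part. It rules out the inference that a detection difference in SFRI could not be addressed in the analysis: events identified through PaTH or claims permit a check that does not depend on the caller. But claims need permission, the planned health-record search is for those lost to follow-up, and none of these sources checks the strength tests.

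Third, the detection losses and encouragement effects have no source in the documents. That is correct, and a reader should not take Step 2 to mean that bias favours exercise; Step 3 shows the opposite is as possible.

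**Conclusion.** The point holds as a gap in the stated design: assessor masking is not provided for, and nothing keeps coaches or randomising staff away from outcome assessment. It matters most for the strength tests and self-reported falls. For SFRI the remaining exposure is unequal elicitation, reduced but not removed by the other data sources.

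The sizes in the working are conditional on the assumed detection ratios and SD shifts, and on 480 per arm. They show that modest differences would be enough to distort the error rate or power; they do not estimate a bias or its sign. The remedy is cheap, so it should be made. It is not a reason to doubt the randomisation or the adjudication.

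**What to change.** Add to 7.2.7 to 7.2.9:

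1. Outcome calls and month-36 tests are done by existing staff who are neither coaches nor the person who randomised that participant, with the allocation field hidden from them in REDCap.
2. The falls and SFRI questions and the strength tests are completed first, with standard wording, before the adverse-event and program-harm questions (10.0) and before any loaned DVD player is returned. Participants are not asked to stay silent about their program, because that could discourage the harm reports that section 10.0 seeks.
3. Any unmasking is recorded.

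Add to 8.3 a sensitivity analysis of SFRI restricted to events identified through PaTH or claims in the same way in both arms.

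The cost is REDCap user rights, rota planning, a fixed question order and one extra analysis, with no new staff. The drawbacks are some scheduling friction and incomplete masking when participants reveal their group. Masking also cannot remove the practice effect from the exercise arm's monthly chair-stand and arm-curl testing (Fitness Testing), which should be stated as a limitation of the strength comparison.
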